5.1.1 Risks Associated with RO7496998 (AT-527)

RO7496998 (AT-527), at once daily doses up to 553 mg (free base), has been evaluated in two clinical studies (AT-01B-001 and AT-01B-002) in healthy volunteers and patients infected with HCV. In the first study, 88 subjects were dosed with blinded study drug (RO7496998 [AT-527] or placebo), with 72 of the 88 subjects receiving active study drug. RO7496998 (AT-527) was well tolerated in both healthy volunteers and patients infected with HCV as either single or multiple doses (seven daily doses) up to 600 mg RO7496998 (AT-527) (equivalent to 553 mg AT-511 free base). In the second study, 10 patients infected with HCV received RO7496998 (AT-527) 550 mg in combination with 60 mg daclatasvir once daily for 8–12 weeks. There were no serious adverse events, dose-limiting toxicities, or premature discontinuations. RO7496998 (AT-527) is currently being evaluated in a Phase II study (AT-03A-001) at 550 mg BID in hospitalized patients with moderate COVID-19 and risk factors for poor outcomes. Safety data from the first 40 patients has not revealed any safety concerns (see Section 1.3). This dose has also been evaluated in healthy volunteers in the AT-03A-002 study, and has been well-tolerated, with no safety concerns (see Section 1.2).

To date, there have been no appreciable patterns of treatment-related or dose-related clinical adverse events or laboratory abnormalities from nonclinical or clinical studies.

Some nucleoside analogues have been associated with mitochondrial toxicity, resulting in damage to liver, muscles, heart, nerve, pancreas, and other organs. Nephrotoxicity has also been associated with the use of some nucleoside analogs (e.g., tenofovir), but is not a broad class effect. The completed nonclinical assessments of RO7496998 (AT-527) indicate no potential for mitochondrial toxicity. To date, there have been no clinical signs of adverse events suggesting mitochondrial toxicity for RO7496998 (AT-527) dosing.

5.1.2 Management of Patients Who Experience Adverse Events

5.1.2.1 Dose Modifications

There will be no dose modification for RO7496998 (AT-527) in this study.

5.1.2.2 Treatment Interruption

Treatment interruptions will not be permitted for RO7496998 (AT-527) in this study.

5.2 SAFETY PARAMETERS AND DEFINITIONS

Safety assessments will consist of monitoring and recording adverse events, including serious adverse events and adverse events of special interest, performing protocol-specified safety laboratory assessments, measuring protocol-specified vital signs, and conducting other protocol-specified tests that are deemed critical to the safety evaluation of the study.

Certain types of events require immediate reporting to the Sponsor, as outlined in Section [5.4](#).

5.2.1 Adverse Events

According to the ICH guideline for Good Clinical Practice, an adverse event is any untoward medical occurrence in a clinical investigation subject administered a pharmaceutical product, regardless of causal attribution. An adverse event can therefore be any of the following:

- Any unfavorable and unintended sign (including an abnormal laboratory finding), symptom, or disease temporally associated with the use of a medicinal product, whether or not considered related to the medicinal product
- Any new disease or exacerbation of an existing disease (a worsening in the character, frequency, or severity of a known condition) (see Sections [5.3.5.8](#) and [5.3.5.9](#) for more information)
- Recurrence of an intermittent medical condition (e.g., headache) not present at baseline
- Any deterioration in a laboratory value or other clinical test (e.g., ECG, X-ray) that is associated with symptoms or leads to a change in study treatment or concomitant treatment or discontinuation from study drug
- Adverse events that are related to a protocol-mandated intervention, including those that occur prior to assignment of study treatment (e.g., screening invasive procedures such as biopsies)

5.2.2 Serious Adverse Events (Immediately Reportable to the Sponsor)

A serious adverse event is any adverse event that meets any of the following criteria:

- Is fatal (i.e., the adverse event actually causes or leads to death)

- Is life threatening (i.e., the adverse event, in the view of the investigator, places the patient at immediate risk of death)

This does not include any adverse event that, had it occurred in a more severe form or was allowed to continue, might have caused death.
- Requires or prolongs inpatient hospitalization (see Section [5.3.5.10](#))
- Results in persistent or significant disability/incapacity (i.e., the adverse event results in substantial disruption of the patient's ability to conduct normal life functions)
- Is a congenital anomaly/birth defect in a neonate/infant born to a mother exposed to study drug
- Is a significant medical event in the investigator's judgment (e.g., may jeopardize the patient or may require medical/surgical intervention to prevent one of the outcomes listed above)

The terms "severe" and "serious" are not synonymous. Severity refers to the intensity of an adverse event (e.g., rated as mild, moderate, or severe, or according to National Cancer Institute Common Terminology Criteria for Adverse Events [NCI CTCAE]; see Section [5.3.3](#)); the event itself may be of relatively minor medical significance (such as severe headache without any further findings).

Severity and seriousness need to be independently assessed for each adverse event recorded on the eCRF.

Serious adverse events are required to be reported by the investigator to the Sponsor immediately (i.e., no more than 24 hours after learning of the event; see Section [5.4.2](#) for reporting instructions).

5.2.3 Adverse Events of Special Interest (Immediately Reportable to the Sponsor)

Adverse events of special interest are required to be reported by the investigator to the Sponsor immediately (i.e., no more than 24 hours after learning of the event; see Section [5.4.2](#) for reporting instructions). Adverse events of special interest for this study are as follows:

- Cases of potential drug-induced liver injury that include an elevated ALT or AST in combination with either an elevated bilirubin or clinical jaundice, as defined by Hy's Law (see Section [5.3.5.6](#))
- Suspected transmission of an infectious agent by the study drug, as defined below

Any organism, virus, or infectious particle (e.g., prion protein transmitting transmissible spongiform encephalopathy), pathogenic or non-pathogenic, is considered an infectious agent. A transmission of an infectious agent may be suspected from clinical symptoms or laboratory findings that indicate an infection in a patient exposed to a medicinal product. This term applies only when a contamination of the study drug is suspected.

5.3 METHODS AND TIMING FOR CAPTURING AND ASSESSING SAFETY PARAMETERS

The investigator is responsible for ensuring that all adverse events (see Section 5.2.1 for definition) are recorded on the Adverse Event eCRF and reported to the Sponsor in accordance with instructions provided in this section and in Sections 5.4–5.6.

For each adverse event recorded on the Adverse Event eCRF, the investigator will make an assessment of seriousness (see Section 5.2.2 for seriousness criteria), severity (see Section 5.3.3), and causality (see Section 5.3.4).

5.3.1 Adverse Event Reporting Period

Investigators will seek information on adverse events at each patient contact.

All adverse events, whether reported by the patient or noted by study personnel, will be recorded in the patient's medical record and on the Adverse Event eCRF.

After informed consent has been obtained but prior to initiation of study drug, only serious adverse events caused by a protocol-mandated intervention (e.g., invasive procedures such as biopsies, discontinuation of medications) should be reported (see Section 5.4.2 for instructions for reporting serious adverse events).

After initiation of study drug, all adverse events will be reported until 28 days after the final dose of study drug.

Instructions for reporting adverse events that occur after the adverse event reporting period are provided in Section 5.6.

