5.3.5.7 Deaths

All deaths that occur during the protocol-specified adverse event reporting period (see Section 5.3.1), regardless of relationship to study drug, must be recorded on the Adverse Event eCRF and immediately reported to the Sponsor (see Section 5.4.2). This includes death attributed to progression of COVID-19.

Death should be considered an outcome and not a distinct event. The event or condition that caused or contributed to the fatal outcome should be recorded as the single medical concept on the Adverse Event eCRF. Generally, only one such event should be reported. If the cause of death is unknown and cannot be ascertained at the time of reporting, "**unexplained death**" should be recorded on the Adverse Event eCRF. If the cause of death later becomes available (e.g., after autopsy), "unexplained death" should be replaced by the established cause of death. The term "**sudden death**" should not be used unless combined with the presumed cause of death (e.g., "sudden cardiac death").

If the death is attributed solely to progression of COVID-19, "COVID-19 progression" should be recorded on the Adverse Event eCRF.

Deaths that occur after the adverse event reporting period should be reported as described in Section 5.6.

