5.4.2.2 Events That Occur after Study Drug Initiation

After initiation of study drug, serious adverse events and adverse events of special interest will be reported until 28 days after the final dose of study drug. Investigators should record all case details that can be gathered immediately (i.e., within 24 hours after learning of the event) on the Adverse Event eCRF and submit the report via the electronic data capture (EDC) system. A report will be generated and sent to Roche Safety Risk Management by the EDC system.

In the event that the EDC system is unavailable, the paper Clinical Trial Serious Adverse Event/Adverse Event of Special Interest Reporting Form provided to investigators should be completed and submitted to the Sponsor or its designee immediately (i.e., no more than 24 hours after learning of the event), either by faxing or by scanning and emailing the form using the fax number or email address provided to investigators. Once the EDC system is available, all information will need to be entered and submitted via the EDC system.

Instructions for reporting serious adverse events that occur >24 days after the final dose of study treatment are provided in Section [5.6](#).

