5.6 ADVERSE EVENTS THAT OCCUR AFTER THE ADVERSE EVENT REPORTING PERIOD

The Sponsor should be notified if the investigator becomes aware of any serious adverse event that occurs after the end of the adverse event reporting period (defined as 28 days after the final dose of study drug), if the event is believed to be related to prior exposure to study drug. These events should be reported through use of the Adverse Event eCRF. However, if the EDC system is not available, the investigator should report

these events directly to the Sponsor or its designee, either by faxing or by scanning and emailing the paper Clinical Trial Serious Adverse Event/Adverse Event of Special Interest Reporting Form using the fax number or email address provided to investigators.

5.7 EXPEDITED REPORTING TO HEALTH AUTHORITIES, INVESTIGATORS, INSTITUTIONAL REVIEW BOARDS, AND ETHICS COMMITTEES

The Sponsor will promptly evaluate all serious adverse events and adverse events of special interest against cumulative product experience to identify and expeditiously communicate possible new safety findings to investigators, IRBs, ECs, and applicable health authorities based on applicable legislation.

To determine reporting requirements for single adverse event cases, the Sponsor will assess the expectedness of these events through use of the reference safety information in the document listed below:

Drug	Document
AT-527	AT-527 Investigator's Brochure

The Sponsor will compare the severity of each event and the cumulative event frequency reported for the study with the severity and frequency reported in the applicable reference document.

Reporting requirements will also be based on the investigator's assessment of causality and seriousness, with allowance for upgrading by the Sponsor as needed.

An aggregate report of any clinically relevant imbalances that do not favor the test product will be submitted to health authorities.

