- Not applicable for a site that has not been granted approval for WGS. Performed only for patients at participating sites who have provided written informed consent to participate. If the sample is not collected at the Day 1 visit for any reason, it may be collected at any later timepoint.
- Study treatment will be administered BID to be taken 12 hours apart for a total of 10 doses. See Section 4.3.2.1 for details.
- Medication (e.g., prescription drugs, over-the-counter drugs, vaccines, herbal or homeopathic remedies, nutritional supplements) and supplemental oxygen used by a patient in addition to protocol-mandated treatment from 7 days (12 months for COVID-19 vaccines) prior to initiation of study drug until the end of study follow-up on Day 33, will be recorded. Any COVID-19 vaccination which has occurred before the patient enrolls into the study or during the study will be recorded in the concomitant medications eCRF, including the product or brand/trade or company manufacturer, if available (examples: Pfizer COVID-19 vaccine, Moderna COVID-19 vaccine) and date administered if known. If not available, report as COVID-19 vaccine.
- After informed consent has been obtained but prior to initiation of study drug, only serious adverse events caused by a protocol-mandated intervention should be reported. After initiation of study drug, all adverse events will be reported until the end of study follow-up telephone call on Day 33.

Appendix 2

Schedule of Pharmacokinetic Samples (for Adults and Adolescents)

Visit	Timepoint	Sample Type
PK sparse sampling ^a		
Day 1 (with reference to 1 st dose)	Predose (-30 min)	RO7496998 (AT-527) PK (plasma)
	1 hour postdose (±30 min)	RO7496998 (AT-527) PK (plasma)
Day 5 (with reference to the morning dose)	Predose (-30 min)	RO7496998 (AT-527) PK (plasma)
	1 hour postdose (±30 min)	RO7496998 (AT-527) PK (plasma)
Day 7	Anytime ^c	RO7496998 (AT-527) PK (plasma)
Optional PK intensive sampling ^b		
Day 1 (with reference to the 1 st dose)	Predose (-30 min)	RO7496998 (AT-527) PK (plasma)
	1 hour postdose (±30 min)	RO7496998 (AT-527) PK (plasma)
	2 hours postdose (±30 min)	RO7496998 (AT-527) PK (plasma)
	4 hours postdose (±30 min)	RO7496998 (AT-527) PK (plasma)
Day 5 (with reference to the morning dose)	Predose (-30 min)	RO7496998 (AT-527) PK (plasma)
	1 hour postdose (±30 min)	RO7496998 (AT-527) PK (plasma)
	2 hours postdose (±30 min)	RO7496998 (AT-527) PK (plasma)
	4 hours postdose (±30 min)	RO7496998 (AT-527) PK (plasma)

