5.4.1.6 Proportion of Patients with All-Cause Mortality

All-cause mortality is defined as an adverse event captured within the clinical database for which there is a non-missing death date (partial date of death will be considered as a death). The statistical method is detailed in Section 5.1.

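### Section 5 ends adverse event and death reporting 28 days after the last dose and Appendix 1 ends it at the Day 33 call; under the Section 5 rule, patients who stop drug early have a window 1 to 4 days shorter

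*Protocol*

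**What the plan says.** Protocol Section 5.3.1 closes general adverse event reporting by reference to the last dose: "After initiation of study drug, all adverse events will be reported until 28 days after the final dose of study drug". Section 5.4.2.2 uses the same anchor for serious events and events of special interest ("serious adverse events and adverse events of special interest will be reported until 28 days after the final dose of study drug"), and Section 5.6 defines the reporting period that way. Section 5.3.5.7 takes its window for deaths from 5.3.1: "All deaths that occur during the protocol-specified adverse event reporting period (see Section 5.3.1), regardless of relationship to study drug, must be recorded". Later deaths are sent to Section 5.6, which asks for notification of a serious event only "if the event is believed to be related to prior exposure to study drug".

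The adverse events footnote to Appendix 1 has a different endpoint: "After initiation of study drug, all adverse events will be reported until the end of study follow-up telephone call on Day 33".

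Stopping drug early does not end follow-up. Section 4.6.1 and Appendix 1 footnote e keep such patients on the assessment schedule to study end.

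The SAP builds several endpoints from these records:
- Mortality (5.4.1.6): "All-cause mortality is defined as an adverse event captured within the clinical database for which there is a non-missing death date".
- COVID-19 hospitalization (5.4.2.4): from serious adverse events.
- Complications (1.2.2 and 5.4.1.3): from events the investigator reports, with adjudication of certain types.
- Post-treatment infection (5.4.2.6): from treatment-emergent adverse events.

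SAP Table 2 runs all four to study end under a treatment-policy strategy, irrespective of treatment completion.

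**The concern.** The estimand promises every patient the same observation period. The Section 5 rule makes the collection period depend on the day of last dose, which is fixed after randomization and which treatment can influence. The SAP can analyse only what sites record, so a long analysis window does not recover an event that a site was not asked to enter.

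Mortality and complications are key secondary endpoints within the SAP's multiplicity procedure. Table 2 also counts death as an event for hospitalization and for medically attended visits. Visits have their own eCRF record, but an unrecorded death could still be missing from that composite.

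Sites could also differ in practice, since neither text says which one governs.

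**Working it through.** **Inputs.** Section 5 anchor: last dose plus 28 days (5.3.1, 5.4.2.2, 5.6). Appendix 1 anchor: the Day 33 call. Planned tenth dose: Day 5 evening if the first dose is before 2 p.m., Day 6 morning if it is after (4.3.2.1). Call window: +3 days in Appendix 1; ±3 days in the synopsis, Protocol 3.1 and SAP 1.2.

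**The plan's own figure.** A 5-day treatment period plus 28 days of follow-up gives 5 + 28 = 33. Day 33 reproduces for a last dose on Day 5.

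**Other last-dose days.** Section 5 closing day = k + 28 for a last dose on Day k; difference = (k + 28) − 33.

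| Last dose | Section 5 closes | Against Day 33 | Share of 33 days lost |
|---|---|---|---|
| Day 1 | Day 29 | −4 | 4/33 = 12.1% |
| Day 2 | Day 30 | −3 | 3/33 = 9.1% |
| Day 3 | Day 31 | −2 | 2/33 = 6.1% |
| Day 4 | Day 32 | −1 | 1/33 = 3.0% |
| Day 5 | Day 33 | 0 | 0 |
| Day 6 | Day 34 | +1 | none |

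**Call timing.** For a Day 6 finisher called on Day 33, the Section 5 window runs 34 − 33 = 1 day past the last contact. With the ±3 wording a call on Day 30 is allowed. For a Day 5 finisher that is 33 − 30 = 3 days before Section 5 reporting closes.

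**What could be missed.** Take a last dose on Day 1 and a first serious event, unrelated to drug, on Day 31. Under Appendix 1 it is recorded (31 < 33). Under Section 5 the period closed on Day 29, and Section 5.6 does not ask for it. The same event in a Day 5 completer is recorded under both rules.

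**Rough size.** The documents give neither the early-stop rate nor the timing of events. Assume that 1% to 10% of patients stop early, and that 2% to 12.1% of events fall on Days 30 to 33 (12.1% = 4/33, an even spread). Treat every early stopper as losing all four days.
- Low: 0.01 × 0.02 = 0.02% of events.
- High: 0.10 × 4/33 = 1.2% of events.

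These are illustrations on assumed inputs. Counting every early stopper at the full four days makes them generous.

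**The case against.** The best reply is that the shortening never happens in practice. Appendix 1 makes no exception for early stoppers, who stay on schedule to study end. Section 5.3.1 itself has investigators seek adverse events at every contact, and the Day 33 call is a contact. SAP 5.1 uses adverse event data until the patient completes or leaves the study, with no 28-day cut. This stands in part: the loss arises only where a site applies Section 5 over Appendix 1. But the conflict remains open, and the rule for deaths points to 5.3.1, not to Appendix 1.

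A reader might infer that a COVID-19 death on Day 31, after a last dose on Day 1, is bound to be left out of the mortality count. The documents do not support that. Section 5.3.5.7 treats death as an outcome of an event, 5.5.1 has each adverse event followed until it resolves or is stable, and 5.4 requires a change in outcome of a serious event to be reported. If the fatal event was already recorded, for example as a hospitalization, the death reaches the database. The exposure is limited to new events.

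A reader might also infer a loss of 7 days from a call on Day 36 (36 − 29). That is not the cost of stopping early: under Section 5 a Day 5 completer's window still closes on Day 33, so the gap between the two patients is at most 33 − 29 = 4 days.

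**Conclusion.** The contradiction is real and lies in current operative text. Its consequence is conditional and small. Under the Section 5 rule, patients with a last dose on Days 1 to 4 have a reporting window 1 to 4 days shorter than Day 33, and a new unrelated fatal or serious event in those days may go unrecorded. Under the Appendix 1 rule there is no dependence on last-dose day. An early stopper whose last dose is on Day 5 loses nothing under either.

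The expected number of missed events is small, about 0.02% to 1.2% on the assumed inputs. Any count of affected patients would need an early-stop rate that the documents do not give. Nor do they show which arm would lose more events, or that patients stopping for worsening or intolerance would have the shortest windows. It is still worth correcting, because it concerns the capture of deaths and serious events for endpoints defined to study end.

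**What to change.** Reconcile Protocol 5.3.1, 5.4.2.2, 5.3.5.7, 5.6 and the Appendix 1 footnote to one window that matches SAP Table 2: all adverse events, serious adverse events and deaths are recorded through the end-of-study contact, for every patient, regardless of when study drug was stopped. A rule taking the later of the Day 33 contact and 28 days after the last dose would not do, because it still depends on last-dose day and can run past the final contact for Day 6 finishers.

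Align the call window at the same time (+3 days in Appendix 1; ±3 days in the synopsis, Protocol 3.1 and SAP 1.2) so that the contact does not fall before reporting closes. If 28 days after the last dose is wanted for everyone, a Day 6 finisher's call would have to be on Day 34 or later, which the +3 wording already allows. Section 5.4.2.2 also refers to 5.6 for serious events more than 24 days after the last dose, against 28 days elsewhere; settle it in the same edit.

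The cost is a sentence in each of these places. No contact is added, since the end-of-study call already takes place.

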5.3.2 Eliciting Adverse Event Information

A consistent methodology of non-directive questioning should be adopted for eliciting adverse event information at all patient evaluation timepoints. Examples of non-directive questions include the following:

"How have you felt since your last study visit?"

"Have you had any new or changed health problems since you were last here?"

